
analyses that examine FTO gene polymorphisms coupled with certain types of dietary intervention which are then associated with changes in nutritional status, body composition, and various inflammatory and hormonal biomarkers in obese subjects (Razquin et al. 2010; De Luis et al. 2012b; De Luis et al. 2015a; De Luis et al. 2015b; Luglio et al. 2017; Di Renzo et al. 2018; De Luis et al. 2020; Parastouei et al. 2020), however, some things are still unclear and limited. Apart from that, no one has ever linked the FTO gene polymorphism to the Balanced Nutrition Diet intervention which is the reference in Indonesia, as well as its effect on cardiovascular risk.
 
Research purposes:
 
General purpose:
 
Examining the Effect of a Balanced Nutritional Diet on Cardiovascular Risk Factors Among Two Types of FTO rs9939609 Gene in Obese Young Women.
 
Special purpose:
 
 1. Analyze differences in the body composition of obese young women between A allele carriers (AC) and TT allele homozygous (TH) groups after Balanced Nutrition Diet intervention 2. Analyze differences in biomarkers of inflammation related to cardiovascular risk (interleukin (IL-6), high-sensitivity CRP (hs-CRP), and adiponectin (ADP)) of obese young women between A allele carriers (AC) and TT allele homozygous (TH) groups after Balanced Nutrition Diet intervention 
Benefits of research:
 
For research subjects, subjects can find out the allele type of the FTO rs9939609 gene themselves as an illustration of genes related to obesity and that can be used as a basis for precision nutrition interventions and will receive nutritional education about balanced nutrition. For the public, it is hoped that this research can increase knowledge about consumption recommendations, especially to normalize nutritional status and reduce the risk of cardiovascular disease by improving health status, especially for young adult women. For educational institutions, it is hoped that this research will provide new scientific evidence in the field of nutrigenomics regarding the interaction of genes and diet influencing the risk of obesity and cardiovascular disease. For the government, it is hoped that it can become a reference for making a policy to reduce obesity cases in Indonesia.
 
Number of Research Subjects:
 
This research uses a hypothesis testing formula for 2 independent samples based on Sastroasmoro & Ismael (2014):
 $n_1 = n_2 = 2 \left[\frac{(Z_{\alpha} + Z_{\beta})S}{X_1 - X_2} \right]^2$ 
The results of calculations using data from previous research (De Luis et al. 2015b) resulted in 7 people. This study used 4 groups, namely 2 control groups and 2 intervention groups, adding an anticipated dropout of 50%, the total number of subjects was at least 44 people or 11 people per group.
 
Information:
 
n = minimum number of subjects
 
Z_{α} = type I error (1.96)
 
Z_{β} = type II error (1.28; power 90)
 
S = standard deviation of the two groups
 
$X_1 - X_2$ = desired clinical difference (difference in weight between Allele T and Allele A)
 
Research by De Luis et al. (2015b) is a consideration for the expected weight loss of subjects in this study, namely assuming a weight loss of ± 1 kg in A allele carriers and ± 0.35 kg in homozygous T subjects after 1 month of intervention with the balanced nutritional diet provided.
 
How to Choose Research Subjects

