	
be conducted using the block randomization method, based on the FTO gene allele. This process will involve two sample randomization blocks: one for A carriers allele and another for T homozygous individuals. Each block will then be randomized and divided into two groups, maintaining a 1:1 ratio between control and dietary intervention. Following randomization, four groups will be formed: two groups receiving the Balanced Nutrition Diet intervention (DAC: A allele carriers + Diet; and DTH: homozygous T allele + Diet), and two control groups (CAC: A allele carriers; and CTH: homozygous T allele). Nutrition education will be provided to all groups. The intervention period will span 4 weeks (28 days), after which a second blood draw will be conducted to gather endline data.
 
The Balanced Nutrition Diet is meticulously designed to supply the body with nutrients in suitable types and quantities, adhering to the principles of food diversity which include variety, balanced proportions, correct amounts, and consistency. Additionally, it emphasizes the "Fill My Plate" guideline, advocating for the consumption of all five food groups daily or at each meal. Portion sizes of the Balanced Nutrition Diet are structured according to the "Balanced Nutrition Tumpeng" model, encompassing 3-4 portions/day of carbohydrates, 2-3 servings/day of fruit, 3-4 servings/day of vegetables, and 2-4 servings/day of side dishes, with restrictions set at 4 tablespoons of sugar, 1 teaspoon of salt, and 5 tablespoons of oil per day, alongside a recommendation of drinking 8 glasses of water daily.
 
During the intervention period, food is provided three times a day - breakfast, lunch, and dinner - following a 28-day menu cycle. The researcher bears the sole responsibility for covering the cost of all food provided to the intervention group during this 28-day period. The Balanced Nutrition Diet offered adheres to specific macronutrient distribution ratios of 45-55% carbohydrates, 15-20% protein, and 20-25% fat, as outlined by Almatsier (2010). Complex carbohydrates, such as whole grains, are prioritized, while protein sources lean towards low-fat options, with half derived from plant-based sources. Monounsaturated and polyunsaturated fats are favored, and organic ingredients are preferred whenever possible.
 
Each meal's composition adheres to the "Fill My Plate" principle, and daily portions follow the "Balanced Nutrition Tumpeng" concept. Specifically, the diet provided by Eat & Fit Catering adheres to certain guidelines, including cooking methods that eschew fire and oil frying in favor of boiling, sautéing, or roasting techniques. Canola oil is the preferred oil, sodium-reduced salt is utilized, and mushroom stock serves as the primary flavouring agent, ensuring both healthfulness and taste. For each subject, energy requirements were calculated according to resting energy expenditure (REE) estimates using Mifflin-St. Jeor Equation (Mifflin et al. 1990). REE is then multiplied by the physical activity level (PAL) according to WHO-FAO that has been obtained.
 
REE (women)= (9.99 x Body Weight) + (6.25 x Height) + (5 x Age) – 161
 
The dietary distribution to subjects occurs three times, facilitated by couriers from the catering party. Should the delivery fall beyond the catering courier's radius, online delivery services will be utilized, with costs borne by the researcher.
 
In contrast, the control group subjects do not adhere to a specific diet regimen. However, they will receive general guidance on healthy eating habits and will be monitored closely. Nonetheless, their energy requirements will still be assessed based on REE and physical activity levels, as previously mentioned.
 
b) Determination of outcome indicators:
 
Evidence shows that compared with TT wild type, the risk allele A FTO rs9939609 showed significantly higher body weight, body mass index, waist circumference, hip circumference, and waist-to-hip ratio (Mangge et al. 2011; Tupikowska-Marzec et al. al. 2019; Mehrdad et al. According to Chrostowska et al. (2013), evidence is growing that the waist-hip circumference ratio is a stronger indicator of cardiovascular disease than body mass index. The meta-analysis of Gholamalizadeh et al. (2020), showed that carriers of the A allele of the FTO rs9939609 polymorphism had a higher fat percentage. The research results of Dorling et al. (2021) showed

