--	---

	
the FTO SNP rs9939609 was associated with changes in REE adjusted for fat mass and lean mass, with the AA allele showing a decrease compared to TT.
 
Several studies have been conducted looking at the relationship between the FTO rs9939609 genotype and interleukin-6 (IL-6) levels, but only a few have shown real differences (de Luis et al. 2012b; Zimmermann et al. 2011; de Luis et al. 2016; Magno et al. 2018; Hosseini et al. 2011). Studies have also been conducted that there is an association of FTO rs9939609 with higher levels of C reactive protein (CRP) (Fisher et al. 2009; Sun et al. 2010; Lappalainen et al. 2011; Tupikowska-Marzec et al. 2019). However, other studies show contradictions (Zimmermann et al. 2011).
 
Research by Mehrdad et al. (2020a) showed that subjects with A allele carriers (AA and AT) had lower adiponectin levels than wild-type subjects (homozygous TT) with homozygous AA allele types having the lowest values although not significantly different. Several other studies also show the same thing in both obese and other types of adult subjects (Saucedo et al. 2017; Isgin-Atici et al. 2021). However, research by de Luis et al. (2016) and Duicu et al. (2016) showed a contrast, namely that adiponectin levels were lower in the TT genotype group compared to the AA genotype group. Based on what has been explained above, several outcome indicators that will be analyzed are waist-hip circumference, mass and total fat percentage &visceral, interleukin-6 levels, hs-CRP levels, and adiponectin levels.
 
Statistical analysis
 
The data obtained were tested statistically using SPSS statistical software for Windows (IBM version 26.0, SPSS Inc., Chicago, Ill., USA). The normality of variable distribution was verified with the Shapiro-Wilk test. Analysis of Variance (ANOVA) was used for all baseline data. Paired samples t-test was used to see changes in calorie intake, macronutrients, BW, BMI, waist circumference, hip circumference, waist-hip ratio, RM, percent total fat, visceral fat, subcutaneous fat, skeletal muscle, IL-6, hs-CRP, and adiponectin between before and after intervention. Data are presented as mean \pm SD and P < 0.05 was considered statistically significant.
 
c) Planned interim analysis: There is no interim analysis in this study.
 
d) Clinical trial termination procedures: Referring to the guidelines for good clinical trials in Indonesia (POM RI 2016), clinical trials are terminated if clinical trial safety problems occur, such as serious undesirable events and serious side effects of the test product. The principal investigator will report the KTDS to the ethics committee no later than 3 days after the incident is discovered. The possibility of KTDS that could occur in this study is that the patient requires hospital treatment as a result of the intervention process.
 
e) Estimated research time required for one subject per procedure: \pm4 weeks
 
f) Ethical issues (state your opinion about the ethical issues this research may encounter):
 
 • Respect for person (respect for human dignity): Subjects in this study took part based on their own conscious choice, there was no element of coercion. Subjects have the right to be protected, including that all Subject data will be kept confidential. • Beneficence(beneficial) Non-maleficence (not harmful): This research optimizes benefits and minimizes harm to subjects. The results of the research will be useful for society. The research design has been made as clear as possible. Researchers have competencies that are appropriate to the research topic to be conducted. • Justice(justice): Subjects are treated the same/or there is no differentiation between subjects.

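### Read literally, special purposes 1 and 2 ask for a carrier-versus-TT difference after the diet, which does not identify a genotype difference in response to the diet

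*Combined protocol and SAP*

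**What the plan says.** In Section B.1 the general purpose is "Examining the Effect of a Balanced Nutritional Diet on Cardiovascular Risk Factors Among Two Types of FTO rs9939609 Gene in Obese Young Women". The first of the two special purposes is to analyse "differences in the body composition of obese young women between A allele carriers (AC) and TT allele homozygous (TH) groups after Balanced Nutrition Diet intervention". Special purpose 2 begins "Analyze differences in biomarkers of inflammation related to cardiovascular risk" and ends with the same contrast between carriers and TT women after the diet. The benefits paragraph promises new evidence "regarding the interaction of genes and diet influencing the risk of obesity and cardiovascular disease".

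The sample-size paragraph in B.1 uses a two-group formula. It defines the difference to be detected as a weight difference between alleles, and then bases it on weight loss, "assuming a weight loss of ± 1 kg in A allele carriers and ± 0.35 kg in homozygous T subjects".

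Section B.9a forms two genotype blocks and randomises diet against control 1:1 within each. This gives DAC, CAC, DTH and CTH, measured at baseline and at 4 weeks.

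Section B.9b reviews what is known without this diet. For body size, "the risk allele A FTO rs9939609 showed significantly higher body weight, body mass index, waist circumference, hip circumference, and waist-to-hip ratio" relative to TT, and a cited meta-analysis found a higher fat percentage in carriers. For the biomarkers the review is mixed. Few studies found real IL-6 differences. Higher CRP is reported, but with contradictory studies. One cited study found that "subjects with A allele carriers (AA and AT) had lower adiponectin levels than wild-type subjects", but the same sentence says this was not significant, and two other studies point the opposite way.

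The Statistical analysis paragraph plans ANOVA for baseline data and paired t-tests of before against after. It names no comparison of change between genotypes or between diet and control.

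**The concern.** Randomisation balances diet against control within a genotype. It does nothing to balance carriers against TT women. A comparison of the two genotypes after the diet therefore mixes any difference that existed beforehand with any difference in response.

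This is a matter of the question asked, and a test alone would not cure it. If someone added a carrier-versus-TT test on endline values, the special purposes would be met as worded, yet the answer would be to a cross-sectional genotype question. A static genotype difference could then be reported as a gene-diet effect and used for the precision-nutrition and policy purposes named in B.1.

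**Working it through.** **Inputs from the plan (B.1).** Z values 1.96 and 1.28; assumed losses 1 kg (carriers) and 0.35 kg (TT), difference 1 − 0.35 = 0.65 kg; 7 per group before dropout; 50% dropout; 11 per group, 44 in total. The SD is not given.

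**The plan's own figure.** 7 × 1.5 = 10.5, rounded up to 11; 11 × 4 = 44. This matches. The 7 cannot be rebuilt without the SD, so it is back-solved from n = 2[(1.96 + 1.28)S/0.65]². A value that rounds up to 7 lies above 6 and at most 7:
- n = 6: S = (0.65/3.24) × √3 = 0.347 kg
- n = 7: S = (0.65/3.24) × √3.5 = 0.375 kg

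An SD this small is plausible for change in weight, not for weight itself. With an assumed between-woman SD of 5 to 15 kg, a 0.65 kg difference in endline weight would have about 5% to 6% power at 11 per group. So the calculation was about change, while the special purposes are worded about the state after the diet.

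**Equal response, starting gap present.** The gap carries through to endline unchanged. For a two-sided 5% endline comparison of DAC with DTH, using a normal approximation with standard error SD × √(2/n), the rejection probabilities are as follows (gaps are assumed):

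| Starting gap (SD) | 11 per group | 7 per group |
|---|---|---|
| 0 | 5.0% | 5.0% |
| 0.2 | 7.6% | 6.6% |
| 0.3 | 10.8% | 8.7% |
| 0.5 | 21.6% | 15.5% |
| 0.8 | 46.7% | 32.2% |

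**Unequal response, as the plan assumes.** Endline gap = starting gap − 0.65 kg. Starting gaps of 0, 0.65, 2 and 3 kg (assumed) give endline gaps of −0.65, 0, +1.35 and +2.35 kg. The response is the same in all four cases. The starting gap sets the size and sign of the result, and at 0.65 kg the response difference disappears.

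**The contrast that isolates response.** (DAC − CAC) − (DTH − CTH) on change removes the starting gap. Its variance is 4S²/n, against 2S²/n for the two-group formula in B.1. Taking 0.65 kg as the interaction and S of 0.347 to 0.375 kg:
- Completers per group for 90% power: 4(3.24 S/0.65)² = 12 to 14, before rounding conventions.
- Power = Φ(0.65/(S√(4/n)) − 1.96). With n = 7: Φ(0.331) = 63% at the larger S and Φ(0.515) = 70% at the smaller. With n = 11: 82% and 87%.
- If the anticipated 50% dropout occurred, 11 × 0.5 = 5.5 per group would remain. That is fewer than 7, and power would be lower still.

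**The case against.** The best reply is that change was meant all along. The special purposes sit in a summary that the form asks to be written for non-doctors. The general purpose is the effect of the diet, the benefits paragraph speaks of gene-diet interaction, the sample size rests on weight loss, and every listed outcome gets a before-after test. This stands as evidence of intent, and it makes the defect one of misaligned wording. It does not close the gap, because the Statistical analysis paragraph never compares change between genotypes or between diet and control. The sample-size paragraph itself moves between a difference in weight and a difference in weight loss.

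A second reply is that entry requires body fat above 35%, which may narrow any starting gap. That is fair, but it does not guarantee balance. The kilogram example is also only illustrative: its starting gaps are assumed, and weight is not among the outcome indicators listed in B.9b, although it is among the variables tested.

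A reader might infer three stronger things that the documents do not support:
- **Carriers and TT women are documented to differ beforehand on all outcomes.** B.9b says so for body size and fat percentage. For IL-6, CRP and adiponectin its evidence is sparse or contradictory, so a gap is possible but not asserted.
- **The endline difference can cancel even when both genotypes respond equally.** It cannot. With equal response the gap persists, and cancellation needs unequal response.
- **The control women (22 of 44) serve no purpose.** That follows only from the narrowest reading of the special purposes. The general purpose, the four-group sample size and the 1:1 allocation all give the controls a role.

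**Conclusion.** The point holds as a mismatch between the special purposes as worded and the question the trial is meant to answer. An endline carrier-versus-TT difference can appear with no difference in response, and a real difference in response can be hidden. For body composition the protocol's own review makes a starting gap likely. For the biomarkers the weakness rests on genotype not being randomised, without a documented gap.

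The size depends on an unknown starting gap. Over assumed gaps of 0.2 to 0.8 SD with equal response, an endline test at 11 per group would reject in 7.6% to 46.7% of trials instead of 5%. The power figures for the replacement contrast rest on the back-solved SD and on 0.65 kg being the full interaction, that is, on control women changing equally in both genotypes. This is a cheap improvement that should be made.

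**What to change.** Reword special purposes 1 and 2 as the difference between carriers and TT women in the effect of the diet on change from baseline: (DAC minus CAC) minus (DTH minus CTH). In the Statistical analysis paragraph, name the matching analysis, a genotype-by-diet term in a baseline-adjusted model, and report the diet-versus-control effect within each genotype beside it. State that a carrier-versus-TT difference in endline values alone will not be read as a gene-diet effect.

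No new groups, visits or samples are needed. The cost is precision. The contrast has twice the variance that the B.1 formula assumes, so the plan should say that the stated 90% power does not apply to it and give the conditional figures: about 63% to 70% with 7 completers per group and 82% to 87% with 11. Baseline adjustment may recover some precision, but the documents give no figure from which to say how much.

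### No post-baseline comparison between groups is planned, for the sized genotype contrast or for diet versus control, and the 50% dropout allowance does not keep the 7 per group behind the 90% power

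*Combined protocol and SAP*

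**What the plan says.** **Sizing (section B, item 1, Number of Research Subjects).** "This research uses a hypothesis testing formula for 2 independent samples". The inputs are 1.96 for the type I error and, for power, "type II error (1.28; power 90". The difference to detect is the "desired clinical difference (difference in weight between Allele T and Allele A". The expected losses are about "1 kg in A allele carriers and ± 0.35 kg in homozygous T subjects after 1 month", both under the diet provided. The result is 7. Then: "This study used 4 groups, namely 2 control groups and 2 intervention groups", and "adding an anticipated dropout of 50%, the total number of subjects was at least 44 people or 11 people per group". S is defined in words but given no value, and the X1 − X2 entered is not stated.

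**Purposes (same item).** The general purpose is the effect of the diet on cardiovascular risk factors in the two FTO types. The first special purpose is to analyse "differences in the body composition of obese young women between A allele carriers (AC) and TT allele homozygous (TH) groups" after the diet. The second asks the same of IL-6, hs-CRP and adiponectin.

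**Design (item 9(a)).** Within each genotype block, subjects are randomised 1:1 to diet or control, giving DAC, DTH, CAC and CTH. All four groups receive nutrition education.

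**Analysis (item 9(b), Statistical analysis).** Three procedures are named: a Shapiro-Wilk check of normality, ANOVA for the baseline data, and paired t-tests of before-after change in intake, anthropometry, body composition and the three biomarkers.

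**The concern.** The sizing, the purposes and the design all point to comparisons between groups. The analysis text has none after baseline. A paired test asks whether the mean changed among the subjects tested. If DAC changes significantly and DTH does not, that does not show that the genotypes differ, which is what both special purposes ask. A before-after change on the diet also cannot be separated from nutrition education or the passage of time without the controls, and those controls provide the only randomised comparison in the trial. A plan followed as written would answer none of its stated purposes, and a between-group test chosen later would be open to the charge of selection.

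The second issue is that 90% is the plan's only power figure. It rests on 7 subjects per group, and the dropout step does not leave 7 at the rate the plan itself anticipates.

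**Working it through.** **1. Purposes against analysis**

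| Question | Sized? | Post-baseline test in item 9(b)? |
|---|---|---|
| A carriers vs TT on the diet (DAC vs DTH) | Yes, for weight | None |
| Diet vs control within genotype (DAC vs CAC, DTH vs CTH) | No | None |
| Before vs after | No | Paired t-test |
| Groups at baseline | No | ANOVA (baseline only) |

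**2. The plan's 44**

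7 × (1 + 0.5) = 10.5, rounded up to 11; 11 × 4 = 44. The stated total reproduces, so the 50% was added to 7.

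- Left after 50% loss: 11 × 0.5 = 5.5, that is 5 or 6 per group.
- Dropout at which 11 still leaves 7: 1 − 7/11 = 36%.
- Needed to keep 7 at 50% dropout: 7/(1 − 0.5) = 14 per group, 14 × 4 = 56 in total.

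**3. Power for DAC vs DTH**

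The plan's formula is n = 2[(1.96 + 1.28)S/(X1 − X2)]². Write m for the unrounded n it gave. If the true SD and true difference equal those entered, the noncentrality with n completers per group is 3.24 × √(n/m). So S and X1 − X2 need not be known separately.

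Assumption: m lies between 6 and 7, rounded up to 7. The key calls n the "minimum number of subjects", which suggests rounding up but does not prove it.

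Two-group t-test, two-sided 5%, noncentral t:

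| Completers, DAC v DTH | m = 6 | m = 7 |
|---|---|---|
| 5 v 5 | 73.6% | 67.1% |
| 5 v 6 | 78.5% | 72.1% |
| 6 v 6 | 83.1% | 77.1% |
| 7 v 7 | 89.4% | 84.4% |
| 11 v 11 | 98.6% | 97.1% |

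The plan's own normal formula at 5.5 per group:

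- m = 6: 3.24 × √(5.5/6) − 1.96 = 1.14, power 87%.
- m = 7: 3.24 × √(5.5/7) − 1.96 = 0.91, power 82%.

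If 7 was instead rounded to the nearest whole number, m could reach 7.5. The t-test figures then drop to 69% (5 v 6) and 82% (7 v 7).

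**4. How far the unprinted S matters**

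If X1 − X2 = 1 − 0.35 = 0.65 kg was entered, S = 0.65 × √(m/2)/3.24, which is 0.35 kg for m = 6 and 0.38 kg for m = 7. Taking 0.65 kg with a larger assumed SD, t-test power is:

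- SD 0.5 kg: 61% with 7 per group, 83% with 11.
- SD 1.0 kg: 20% with 7 per group, 31% with 11.

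**5. Diet-by-genotype contrast, for scale**

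(DAC − CAC) − (DTH − CTH) has variance 4S²/n against 2S²/n for DAC vs DTH. Suppose the effect has the same size, which also assumes no genotype difference in the controls. The noncentrality is then 3.24 × √(n/(2m)) on 4n − 4 degrees of freedom. Power is 80–86% with 11 per group, 59–66% with 7 and 48–55% with 5.5.

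**The case against.** The strongest reply is that the trial enrols 11 per group, not 7, and that with everyone retained the power is 97–99%. That stands. A reader might infer that the study is simply too small for its genotype contrast; the documents do not support this. The shortfall appears only at the dropout the plan anticipates and, in one favourable corner (6 left in each group and an unrounded n of exactly 6), the plan's normal formula still returns 90%.

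A reader might also infer that the 90% fails even with 7 completers. The two-group t-test gives 84–89%, but that is the ordinary gap between a normal formula and a t-test. Pooling the variance over all four groups gives 88–92%. This is minor and depends on a test the plan does not name. After dropout, pooling gives 78–84% at 5.5 per group, so that shortfall remains.

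It would be too strong to say that the controls are never compared with anyone, since the baseline ANOVA may include them. What is missing is any comparison after baseline. It would also be too strong to say that the power figures hold whatever the SD is. They hold only if the true SD equals the S that was entered, and S is not printed.

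Finally, the 50% could be defended as a mark-up on 7 and not a loss rate. The plan calls it an anticipated dropout, and a 50% mark-up covers only 36% loss, so the wording needs correcting either way.

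**Conclusion.** The concern holds in two parts.

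1. **Missing comparisons.** This is the more serious part and needs no assumption about S. The analysis text contains no post-baseline comparison between groups. Neither the genotype difference on the diet nor the randomised diet effect is tested, and before-after tests cannot stand in for either.

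2. **Dropout and power.** The 50% was applied by multiplication, so the stated dropout leaves fewer than the 7 per group on which the 90% rests. The 90% should not be quoted for that situation. The range of 67–83% covers 5 or 6 completers per group and is conditional on a common SD and a true difference equal to the values entered, with an unrounded n of 6 to 7. A larger true SD lowers every figure.

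The 90% refers to DAC vs DTH on weight only. No contrast with the controls was sized.

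**What to change.** **Item 9(b), Statistical analysis**

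- For weight and each listed body-composition and biomarker outcome, add a between-group comparison of change from baseline for DAC vs DTH, and for diet vs control within each genotype (DAC vs CAC, DTH vs CTH). Name one method in advance: an independent-samples t-test of change, or ANCOVA adjusted for baseline.
- Report (DAC − CAC) − (DTH − CTH) as an estimate with a 95% confidence interval, labelled precision-limited.
- Keep the paired tests as descriptive.

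**Item 1, Number of Research Subjects**

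- Keep 44 subjects. Print S, the X1 − X2 used and the unrounded n.
- Correct the dropout statement: 11 per group retains 7 at up to 36% dropout.
- Restate the power for DAC vs DTH at the completers expected under 50% dropout, computed from the sponsor's own S. The figures above are a check and should not be copied in.
- State that contrasts with the control groups were not sized.

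**Cost.** Rewording and a few added lines of analysis. No extra subjects, visits or assays are needed, because all four groups are already due for measurement at baseline and endline. The downside is a less favourable stated power and a little more analysis.

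### The dropout allowance adds 50% to 7 per group to reach 11, but losing 50% of 11 leaves 5–6 completers, below the plan's own minimum of 7

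*Combined protocol and SAP*

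**What the plan says.** Section B.1, Number of Research Subjects, is the only sample-size justification in the text available. It opens with "This research uses a hypothesis testing formula for 2 independent samples" and sets n1 = n2. The listed terms include "n = minimum number of subjects", "type I error (1.96" (a two-sided 5% level) and "type II error (1.28; power 90", that is, 90% power. The assumed effect is given by "assuming a weight loss of ± 1 kg in A allele carriers and ± 0.35 kg in homozygous T subjects", a difference of 0.65 kg. The spread appears only as "S = standard deviation of the two groups", with no value.

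The calculation "resulted in 7 people". The plan then names four groups (two control, two intervention) and concludes: "adding an anticipated dropout of 50%, the total number of subjects was at least 44 people or 11 people per group". The step from 7 to 11 is not shown.

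**The concern.** A dropout rate is the share of enrolled subjects who are lost, so the minimum has to be divided by the share who stay. Adding the same percentage to the minimum gives a smaller number, and the gap between the two methods widens as the rate rises. At 50% it is large.

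The plan offers 44 as enough to satisfy its calculation after the loss it anticipates. If 44 is not enough, every group is expected to finish below the stated minimum, and the 90% power resting on that minimum is unsupported. A reader who met a null genotype difference would wrongly take the trial to have been sized for that loss.

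**Working it through.** **Inputs, all from section B.1:** minimum n = 7; anticipated dropout = 50%; groups = 4; planned enrolment = 11 per group, 44 in total; Z values 1.96 and 1.28 (sum 3.24); difference 1 − 0.35 = 0.65 kg. The 7 is read as per group because the formula is for n1 = n2 and because 7 per group, inflated and multiplied by four, gives the plan's total.

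**Step 1. Reproduce the plan.** 7 × (1 + 0.5) = 10.5, rounded up to 11; 11 × 4 = 44. Both printed figures match. The alternative, 7/(1 − 0.5) = 14 and 14 × 4 = 56, does not. The factor 1.5 is therefore inferred, but it reproduces both figures exactly.

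**Step 2. Apply the plan's own dropout to its own enrolment.** 11 × (1 − 0.5) = 5.5 per group; 5.5 × 4 = 22 completers, against 7 × 4 = 28 required.

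**Step 3. Find the dropout that 11 can absorb.** 1 − 7/11 = 4/11 = 36.4%.

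**Step 4. Chance of keeping 7.** If each subject independently has a 50% chance of dropping out, the probability that at least 7 of 11 complete is 0.274 for one group. For both diet groups it is 0.274² = 0.075.

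**Step 5. Power at the reduced number.** S is not printed, but the plan's formula makes it unnecessary. Let n0 be the unrounded result. From n0 = 2[3.24 × S/difference]², the standardised difference is 3.24 × √(2/n0). Power with n completers per group is then

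Φ(3.24 × √(n/n0) − 1.96).

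For 11 completers split 5 v 6, n is replaced by 2 × 5 × 6/11 = 5.45. *Assumption:* n0 was rounded up to 7, so it lies between 6 and 7. With a 0.65 kg difference this corresponds to S = (0.65/3.24) × √(n0/2) = 0.347 to 0.375 kg.

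| Completers per group | Normal, n0 = 7 | Normal, n0 = 6 | t-test, n0 = 7 | t-test, n0 = 6 |
|---|---|---|---|---|
| 5 v 5 | 78.2% | 84.1% | 67.1% | 73.6% |
| 5 v 6 | 81.6% | 87.1% | 72.1% | 78.5% |
| 6 v 6 | 85.1% | 90.0% | 77.1% | 83.1% |
| 7 v 7 | 90.0% | 93.8% | 84.4% | 89.4% |

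From 7 v 7 to 5 v 6 the loss, from unrounded values, is 6.8 to 8.4 points by the normal formula and 10.9 to 12.3 points by the t-test.

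**The case against.** The arithmetic is hard to dispute, so the case for the plan is about reading and weight.

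- **The 50% may be an add-on.** The sentence speaks of adding, and a 50% add-on to 7 gives exactly 11. On that reading 11 was intended and the fault is a mislabelled allowance. This is possible, but the plan calls the figure anticipated dropout. If an add-on was meant, the stated rate is wrong and the sentence must still change.
- **The completer count is an expectation.** This stands: 5.5 per group assumes equal loss in all groups, and diet and control groups may differ.
- **The target is a floor, and missing data may be recovered.** The general part of the form, just before its item 8, allows incomplete data to be collected remotely or at the subject's place. Neither point is a replacement rule or a second dropout rate. The budget (item 11 of the same part) shows no slack: it prices 40 DNA isolations, 42 PCR runs and diets for 20.
- **The power loss is conditional and moderate.** This stands. Ordinary rounding instead of rounding up would put n0 between 6.5 and 7.5, and power at 5 v 6 at about 79–84% by the normal formula. The t-test gives only 84–89% even with 7 per group, so part of its distance from 90% comes from the normal approximation. Only the like-for-like loss belongs to this point.
- **The formula's contrast is not a listed analysis.** The Statistical analysis text in item 9(b) of section B lists ANOVA for baseline data and paired t-tests for change. The power figures here describe the two-sample contrast that the formula is for, not those tests. That mismatch is a separate matter and does not repair this one.

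**Conclusion.** The concern holds. The stated minimum, dropout rate and enrolment cannot all be right together: 50% dropout calls for 14 per group, the plan has 11, and 11 tolerates at most 36%. This part needs no standard deviation, effect size or outside source. It rests only on reading 7 as per group and 50% as the share of enrolled subjects lost.

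The effect on power is less certain because it depends on the unrounded n. With that between 6 and 7, and losses spread evenly, the expected completers support about 82–87% power by the plan's own formula, or about 72–78% by a two-sample t-test, where the plan claims 90%. This is a moderate loss, but it affects the only justification given for the trial's size, so the text must be corrected.

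**What to change.** Show the inflation in section B.1 as n/(1 − dropout), keep enrolment at 44, and make one of two statements:

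- **(a)** 11 per group preserves 7 completers only if dropout is no more than 36%, with the sponsor's reason for expecting that rate in place of 50%; or
- **(b)** dropout of 50% is still anticipated, 5–6 completers per group are expected, and the power at that number is restated from the S and the difference used in the formula, both printed.

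Either takes one or two sentences and no extra subjects. The price is a less favourable statement: (a) lowers the dropout the plan claims to withstand and needs a justification, while (b) lowers the stated power. Neither delivers 7 completers per group at 50% dropout. That would take 56 subjects, 12 more than planned, and the corrected text should not imply otherwise.
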